Appendix 3. CLAIMS-BASED INDEX OF RA SEVERITY (CIRAS)

	1
Measure ⁶	Score
Age(continuous)	-0.066
Gender	-0.092
0: male	
1: female	
Inflammatory marker test ordered 0: no	0.60
1: yes	
Rehabilitation visit 0: no	0.69
1: yes	
Rheumatoid factor test 0: no	2.1
1: yes	
Felty's syndrome 0: no	2.3
1: yes	
Number of platelet counts ordered $0 = 0$ visits	0.42
1 = 1 visit	
2 = 2 visits	
3 = 3 visits	
4 = 4 + visits	
Number of chemistry panels ordered $0 = 0$	-0.14
panels	
1 = 1 panel	
2 = 2 panels	
3 = 3 panels	
4 = 4 panels	
5 = 5 + panels	
Rheumatologist visit count $1 = 0$ visits	0.52
2 = 1-4 visits	
3 = 5 + visits	
Intercept	6.5
	 

Number of platelet counts, chemistry panels, and rheumatologist visits are counted 1 per person per day.

Codes for CIRAS Calculation

	Codes	Visits/Tests
Rehabilitation	OT/PT Codes: G0151,G0152,G0157,G0158, G0159,G0160,S9129,S9131,97001,97002,970 03,97004	Occupational therapy/physical therapy visits
Rheumatoid	CPT 86430,86431	Rheumatoid Factor Test Qual,
Factor		Rheumatoid Factor Test Quant
Felty's syndrome	ICD-9/10: 714.1, M0500	
Platelet counts	CPT: 85049	Automated platelet count
Chemistry panels	CPT: 80053, 82248, 82465, 82977, 83540, 83615, 84100, 84478, 84550	A/G Ratio, Albumin, Alkaline Phosphatase, Alanine Aminotransferase, Asparate Aminotransferase, Direct and Total Bilirubin, BUN/Creatinine Ratio, Calcium, Carbon Dioxide, Chloride, Cholesterol, Creatinine, Gamma Glutamyltransferase, Globulin, Glucose, Iron, Lactate Dehydrogenase, Phosphate, Potassium, Total Protein, Sodium, Triglycerides, Urea Nitrogen (BUN), Uric Acid

Appendix 4. COMORBIDITIES OF INTEREST

Disease	ICD-9 codes	ICD-10 codes
Cardiovascular Disease		
Ischemic heart disease	411.xx 413.xx 414.xx	I241, I200, I240, I248, I208, I201, I209 I2582, I2583, I2584, I255, I259, I2589, I2510, I25810, I25811, I2 5812, I253, I2541, I2542, I253
Congestive heart failure	428.xx	1509, 1501, 15020-5023, 1503-5033, 15040-5043
Myocardial infarction	410.xx,	I2109, I2119, I2111, I2129, I213, I214
Peripheral vascular disease	441.xx, 443.9x	1711-716, 1718-719, 17100-7103, 1739
	PROC codes: 38.13, 38.18, 38.48	
Hypertension	401.xx, 437.2x	I10,I169, I674
Dyslipidemia	272.xx	E7800-7801, E781-786, E881, E770-771, E7521-7522, E75249, E7881, E7889, E8889, E789
Diabetes	250.xx	E119,E109, E1165, E1065, E1169, E1310 E1010, E1165, E1169,E1065, E1100, E1101, E1069, E1100, E1165, E1069, E11641, E1011, E10641, E1101, E1165, E1011, E1065, E1129, E1029, E1121, E1165, E1021, E1065, E1136, E1139, E11311 E11319, E1036, E1037X1, E1037X2, E1037X3, E1037X9, E1039,E10311, E10319, E1136, E1139, E1165 E11311, E11319, E1036, E1039, E1065, E10311, E10319, E1140, E1040, E1140, E1165, E1040, E1065, E1151, E1051, E1151, E1165, E1051, E1065, E1165. E1169, E11618, E11620, E11621, E11622, E11628, E11630, E11638 E11649, E1065, E1069, E10618, E10620, E10621,E10622, E10628, E10630, E10638, E10649, E1165, E1169, E1065, E1069 E118, E108, E118, E1165, E108, E1065
Depression	300.4x, 309.0x, 309.1x, 309.28, 311.xx	F341, F4321, F4323, F329
COPD	491.21	J441
Asthma	493.xx	J4520, J4522, J4521, J4520, J4522, J4521, J449, J440, J441, J45990 J45991, J45909, J45998, J45902, J45901

Disease	ICD-9 codes	ICD-10 codes
Kidney disease		E1129,E1029,E121,E1165,E1021,E1065 I129, I120, I1310, I130, I1311, I132, I150, N003, N013, N009, N09, N008, N044, N022, N043, NO40, N049, N032, N033, N035, N038, N039, N08, N048,N05,N052,N055, N059,N171,N172,N059, N08,N058, N170, N171, N172,N178, N179, N181-186, N189, N19, N269, N250, N251, N2581, N2589, N270, N271, N279, Q602, Q605, Q619,Q6100,Q6101,Q613, Q612, Q6119, Q614, Q615,Q615,Q618,Q610, R803, R809, Z992, Z9115, Z4931, Z4901, Z4902, Z4932, Z4931
Liver disease	1	B182, B1921, G9340, G9341, G9349, I6783, I8501, I8500, I8511, I8510, K7290, K7291, K766, K767, R17, R168, C220, C222, C227, C228, C221, C229, Z944, J64
Anxiety	300.02, 293.84, 309.21, 300.0, 300.00,	F410, F422,F423, F428, F429, F4310, F4312, F4010, F4001, F4002, F409, F4001, F4002, F4010, F408, F40218, F40240, F40241, F409, F411, F064, F930, F419, F410, F411, F418, F99, F489, F449, F444, F446, F440, F441, F4481, F449, F4489, F6811, F688,R42, R000, R002, R064, R0602, R063, R0600, R0609, R0683, R0689
Sleep disorders		F519, F5102, F5109, F5101, F5103, F5109, F5119, F5111, F5112, F5119, F518, F513, F518, G479, G4730, G4700, G4730, G4710, G4720, G478, G4730, F518, G478, R0681, Z72820
Interstitial lung disease	516.9	J84.9

	GPI Codes ^	HCPCS	Prednisone Eq Dose
SYSTEMIC GLUCOCORTIC	OIDS		
High Potency			
betamethasone	22100010	J7624	0.60
dexamethasone	22100020	J1094, J1095, J1100, J8540, Q0137, Q0138, S0173	0.75
Medium Potency			
Fludrocortisone	2220003010		n/a
methylprednisolone	22100030	J1020, J1030, J1040, J2920, J2930, J7509	4
prednisolone	22100045	J1680, J2640, J2650, J7510	5
prednisone	22100040	J1690, J7506, K0125	5
Triamcinolone	22100050	J3300, J3301, J3302, J3303	4
Low Potency			
Cortisone	22100015	J0810	25
Hydrocortisone	22100025		20
NSAIDs/Salicylates	6610, 66998, 6410	J1885, J1130, J0131, C9283, J1741, C9279	N/A
Opioids			N/A
Strong (morphine, methadone, fentanyl, hydromorphone, oxymorphone, oxycodone, hydrocodone, buprenorphine, butrophanol, nalbuphine, levorphanol)	65100055,655100050, 65100025,65100035,6 5100080,6500075,651 00030,65200010,6520 0020,65200030,65100 040	J2275 ,Q9974 S0093 , J1230 ,S0109 J1170 S0092 J2410	N/A

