Comorbidities of interest	Baseline Characteristic	All	 0/1 flags will be created to identify the presence of the following comorbidities during the 12-month baseline period (see Appendix 4). Cardiovascular diseases. Chronic obstructive pulmonary disease (COPD). Asthma. Kidney disease. Diabetes. Depression. Anxiety. Liver disease. Sleep disorders. Hypertension. Hyperlipidemia. Interstitial lung disease.

Variable	Role	Data source(s)	Operational definition
Cumulative OOP Costs pre-index	Baseline Characteristic	All	The total, pharmacy and medical OOP costs (deductible+copay+coinsurance) resource use from January 1 of index year through Index.
Index Date OOP costs	Baseline Characteristic	All	Total, pharmacy (excluding index medication) and medical OOP costs on index date.
Index Medication (Table	4)		
Index Prescriber	Baseline Characteristic	All	Top 5 index medication prescriber specialties and other or unknown will be identified.
Index month/year	Baseline Characteristic	All	The month and year of the patient's index date (start of TOFA, ETN, ADA) will be identified.
Index Medication OOP costs	Baseline Characteristic	All	The index medication pharmacy OOP costs (deductible+copay+coinsurance) will be identified for the first index medication rx and cumulative by month (1-12) of follow-up (only looking at pharmacy claims here noting index event is a prescription fill).
Index combination vs. monotherapy regimen status	Baseline Characteristic	All	Patients with a use of one of the 4 main NB- DMARDs (injectable and oral MTX, SSZ, HCQ, LEF) within 90 days on or after the index date will be considered as being treated with combination therapy regimen, others will be classified as monotherapy. For monotherapy, will evaluate 6-mos pre-index use of each of the four main and other NB- DMARDs. For combination regiment, will stratify by 6 mos pre-index use of the four main and other NB-DMARDs.
Post-Index Treatment Pa	tterns (Table 4)		
Treatment Persistence (5 groups)	Outcome	All	Persistent with the index medication will be defined as not having a gap in therapy of at least 60 days between fills/admins. For retail pharmacy (rx) claims the day supply will be utilized and rounded to the nearest 28-day supply for ETN and ADA and 30- day supply for TOFA. For subcutaneous ETN and ADA administrations, a 28-day supply will be assumed.

Variable	Role	Data source(s)	Operational definition

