- Costs from other payers are of importance for older patients dually eligible for commercial and Medicare coverage. Payments from Medicare (and other payers) will be estimated based on coordination of benefits information obtained by the health plan in its usual course of business. This study will incorporate the amounts estimated to be paid by other payers for a total paid or allowable amount.¹⁷
- All-cause health care costs- calculated as total of medical (outpatient, inpatient and ED) visits regardless of reason and all prescription costs.
- **RA-related health care costs-** RA-related health care costs will be calculated as total medical and treatment costs related to RA.
 - RA-related medical costs will include costs for outpatient, inpatient and ED vists with an RA diagnosis in any claim position
 - For outpatient visits with an RA diagnosis and administration of an RArelated treatment (see below), the non-administration costs will be characterized as part of RA-related Medical costs and the administration costs will be part of RA-related Treatment costs below.
 - Outpatient visits without an RA diagnosis, but with administration of an RArelated treatment will not be included in the RA-related Medical costs, but will be evaluated for administration costs as part of RA-relatedTreatment costs below.

Note: given variability in capture of HCPCS codes in inpatient setting across databases, RA- related treatement costs are limited to outpatient visits only.

- RA-related treatment costs will include the cost of:
 - outpatient administration of bDMARDs, NB-DMARDs, corticosterioids, NSAIDS, and opioids based on HCPCS codes regardless of RA diagnosis on claim, AND,
 - cost of prescription fills for TOFA/ADA, ETN, other advanced therapies, NB-DMARDs, corticosterioids, NSAIDS, and opioids.

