8.7.4. Multivariate Analysis

To control for possible confounding of the relationship between the outcomes and independent variable of interest, select objectives will be conducted utilizing multivariable methods as described above.

Final outcomes for multivariate analysis will be selected after review of descriptive results. Possible outcomes of interest include: total all-cause health care cost, total RA-related health care cost, cost of bDMARDs/tofacitinib/administration/NB-DMARDS, medication effectiveness (yes vs. no).

For each model, specific predictors to be included will be determined based upon clinical rationale and statistical significance. Variables listed in Section 8.3 will be considered for inclusion in the multivariable models. Additional variables identified throughout the course of the study will also be considered. Following standard procedure, regression diagnostics will be performed for each model to assess goodness of fit and violations of model assumptions (eg, multicollinearity, heteroskedasticity). When there are violations of the model, programmers will note them and make appropriate corrections to the data (ie, typically through transformation of either the independent or dependent variables) or in the method of estimation.

In particular, generalized linear models will be fit, using appropriate distributions and links for the nature of the data (eg, normally-distributed data with identity link, binary data and logit link). Results will be displayed on the original scale (that is, the inverse link). If sufficient sample size, tofacitinib IR and tofacitinib XR will be treated as separate groups. That is, contrast statements will be used to average the two groups when comparing to bDMARDs. Point estimates (that is, mean differences, ratios, odds ratios), 95 percent confidence intervals, and p- values will be presented for contrasts; ANOVA table will be presented to display the strength of the independent variables, including point estimates and p-values.

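### Two of the 11 strong-opioid GPI codes in Appendix 5 are malformed as printed and need checking; the J44x overlap between the COPD and asthma lists needs the sponsor's confirmation

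*Combined protocol and SAP*

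**What the plan says.** **Opioid codes.** The strong-opioid row of Appendix 5 names 11 drugs, "Strong (morphine, methadone, fentanyl, hydromorphone, oxymorphone, oxycodone, hydrocodone, buprenorphine, butrophanol, nalbuphine, levorphanol", and prints 11 GPI codes: "65100055,655100050, 65100025,65100035,6 5100080,6500075,651 00030,65200010,6520 0020,65200030,65100 040". The stray spaces are line wraps in the table cell. The appendix gives MediSpan as the source of its GPI codes. Section 8.3.1 counts paid prescriptions for weak and strong opioids in RA-related pharmacy utilization, and RA-related treatment cost includes the "cost of prescription fills for TOFA/ADA, ETN, other advanced therapies, NB-DMARDs, corticosterioids, NSAIDS, and opioids".

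**Comorbidity codes.** Appendix 4 gives COPD one code in each version: "COPD 491.21 J441". Asthma is 493.xx in ICD-9, and its ICD-10 list contains "J449, J440, J441, J45990". On how the lists are used, Section 8.3 says "0/1 flags will be created to identify the presence of the following comorbidities during the 12-month baseline period", with asthma and COPD as separate items. Section 8.7.4 adds: "Variables listed in Section 8.3 will be considered for inclusion in the multivariable models".

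**The concern.** Claims codes are matched literally. A code with a digit too many or too few does not fail visibly; it returns no records, and the drug is missing from the count. RA-related utilization and cost are secondary outcomes, and total RA-related cost is a possible outcome for multivariable modelling (Section 8.7.4), so a silent omission there would reach reported results.

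The overlap between COPD and asthma raises a different question. If one ICD-10 code triggers both flags while the ICD-9 codes keep them apart, the relation between the two flags depends on which code version a patient's baseline year used. Both flags are reported at baseline and are candidate covariates.

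**Working it through.** No sample size, power or alpha figure is involved. The check is a count and comparison of the printed codes.

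**Step 1. Strong-opioid codes, wraps rejoined, paired with drugs by list order (Appendix 5).**

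| # | Code | Digits | Drug by position |
|---|---|---|---|
| 1 | 65100055 | 8 | morphine |
| 2 | **655100050** | **9** | methadone |
| 3 | 65100025 | 8 | fentanyl |
| 4 | 65100035 | 8 | hydromorphone |
| 5 | 65100080 | 8 | oxymorphone |
| 6 | **6500075** | **7** | oxycodone |
| 7 | 65100030 | 8 | hydrocodone |
| 8 | 65200010 | 8 | buprenorphine |
| 9 | 65200020 | 8 | butorphanol |
| 10 | 65200030 | 8 | nalbuphine |
| 11 | 65100040 | 8 | levorphanol |

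Six codes begin 65100 and three begin 65200, so 6 + 3 = 9 of 11 fit one pattern. The weak-opioid row supports it: five of its six codes have 8 digits with the same stems, and the sixth is the short code 6599.

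**Step 2. Would prefix matching rescue them?** No. The irregular codes begin 6551 and 6500, not 6510 or 6520, so neither can match a code built like the other nine, at full length or by prefix.

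**Step 3. Could the PDF reading have caused it?** Each full wrapped line of the cell holds 17 digits and 2 commas, 19 characters. The line with 6500075 is 7 + 1 + 7 + 1 + 3 = 19, so a lost digit there would have made it 20, longer than its neighbours. The same check is weaker for 655100050, because its line ends at a comma followed by a space.

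**Step 4. Nearest codes that fit the pattern.** Deleting one digit from 655100050 gives one candidate, 65100050. Adding one digit to 6500075 gives two, 65100075 and 65200075. The second entry therefore cannot be repaired from the list alone.

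**Step 5. COPD against asthma (Appendix 4).** The asthma ICD-10 list has 15 entries, 12 of them distinct: 9 beginning J45, plus J440, J441 and J449. The COPD ICD-10 list is J441 alone, so 1 of 1 COPD codes lies inside the asthma list. A patient with only J440 or J449 is flagged for asthma and not COPD. Under ICD-9, 491.21 is not within 493.xx, so the overlap is 0.

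**The case against.** **On the opioids.**

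- Code length alone proves nothing, because Appendix 5 has other GPI entries that are not 8 digits long (6610, 66998, 6599, 2220003010). That is true, but the two irregular codes also break the stem that the other nine share.
- Linking them to methadone and oxycodone rests on list order, which is not certain. In the weak row, combinations are named third of six, while 6599 stands last of six. If 6599 is the combination code, that row does not keep the order.
- A reader might infer that two ingredients vanish from the counts altogether. The documents do not support this. The weak-opioid row covers combination products, apparently through 6599, and administrations are captured separately by HCPCS code.
- A reader might also infer that opioid use has in fact been miscounted. That follows only if the list was programmed as printed, and the programmed list is not in the documents. Section 8.8 provides for verification by a second programmer. This helps less if both work from the same appendix.

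**On asthma and COPD.** A reader might infer that the J44x codes are plain errors, that everyone with only those codes is a false asthma case, and that they should be deleted. The documents do not support that. The list prints J4520, J4522, J4521, repeats that triplet, and then gives J449, J440, J441. This is consistent with a deliberate code-by-code conversion of 493.xx, although no crosswalk is shown. If so, deletion would leave part of the ICD-9 asthma definition without an ICD-10 counterpart. Moving J440 and J449 to COPD would widen its ICD-10 definition from one code to three while ICD-9 stayed at one. Either step could create a shift between code versions. The flags are not declared mutually exclusive, and the kidney and diabetes lists also share codes (for example E1129 and E1065). This objection stands, so the overlap is a query and not a finding of error.

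**Conclusion.** The two GPI entries are wrong as written, and the point is minor. Two of 11 strong-opioid codes would match nothing built like the other nine. If they were used as printed, the corresponding pharmacy fills, outside combination products under 6599, would be missing from RA-related pharmacy utilization and treatment cost.

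The size cannot be computed, because the documents give no fill counts or prices. The same list applies to every cohort and to both the pre- and post-index periods, so the effect on a comparison depends on how far use of the affected drugs differs between cohorts or changes over time; its direction is unknown. All-cause cost takes in all prescriptions and does not depend on this list. A reader might extend the point to the primary result, but persistence is built from fills and administrations of the advanced therapies and does not use these codes.

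The conclusion assumes literal or prefix matching on the printed codes. Naming the drugs also assumes that list order holds.

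For COPD and asthma, the overlap is a fact, but whether it is intended cannot be settled from the documents. No false-positive rate can be given.

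**What to change.** 1. Check 655100050 and 6500075 against the MediSpan source and correct Appendix 5. For the second, the source must decide between 65100075 and 65200075, if it is either.
2. Check the programmed code list. Version 1.1 is dated 7 October 2019, after the planned end of data collection (30 June 2019) and the planned final report (30 September 2019), so correcting the appendix alone may come too late. If the programmed list matches the printed one, rerun the RA-related utilization and cost tables and any model of RA-related cost. If it already holds the right codes, only the appendix changes.
3. Ask the sponsor whether J440, J441 and J449 are meant to count as asthma, and whether J441 is meant to set both flags. Record the answer, and keep the ICD-9 and ICD-10 definitions of each flag consistent with each other. Do not delete or move the codes before that is settled.

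The cost is a short lookup and, at most, a rerun of a few secondary tables. Nothing in the design changes.

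### Appendix 4 lets two codes that recur throughout its diabetes row (E1165, E1065) set the kidney disease flag on their own, so that flag is partly a second diabetes flag

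*Combined protocol and SAP*

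**What the plan says.** In the Section 8.3 variables table, the entry for comorbidities of interest states that "0/1 flags will be created to identify the presence of the following comorbidities during the 12-month baseline period" and refers to Appendix 4 for the codes. Kidney disease, diabetes and anxiety are listed as separate conditions. Neither that entry nor the appendix asks for a second claim or a paired code.

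In Appendix 4 the ICD-10 list for kidney disease begins "E1129,E1029,E121,E1165,E1021,E1065". The diabetes row contains almost the same run, "E1129, E1029, E1121, E1165, E1021, E1065". It also places E1165 and E1065 elsewhere, for example in "E119,E109, E1165, E1065, E1169", "E1136, E1139, E1165 E11311, E11319, E1036, E1039, E1065, E10311, E10319", "E1140, E1040, E1140, E1165, E1040, E1065, E1151, E1051, E1151, E1165, E1051, E1065" and "E118, E108, E118, E1165, E108, E1065".

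The anxiety ICD-10 list ends "R42, R000, R002, R064, R0602, R063, R0600, R0609, R0683, R0689".

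The comorbidity flags are reported in Table 3. Section 8.7.2.1 says that cohort differences in such characteristics will inform the multivariable work. Section 8.7.4 makes every Section 8.3 variable a candidate predictor, chosen on clinical rationale and statistical significance.

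**The concern.** A code that the appendix attaches to nearly every diabetes cluster cannot single out renal disease. Placed in the kidney row and applied singly, it turns some diabetics without any renal code into kidney disease cases. The two flags then share trigger codes by construction. Table 3 would overstate kidney disease, and a model containing the kidney flag would adjust partly for diabetes under another name. The multicollinearity check in Section 8.7.4 might show the overlap but would not trace it to the code list.

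The anxiety list raises a weaker question of the same kind: any one of its R codes sets the flag with no F code present.

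**Working it through.** **Code count.** The diabetes ICD-10 cell, as printed, has 93 entries and 51 distinct codes. The six E codes that open the kidney row occur in it as follows:

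| Kidney-row code | Times in diabetes row |
|---|---|
| E1165 | 11 |
| E1065 | 10 |
| E1129 | 1 |
| E1029 | 1 |
| E1021 | 1 |
| E121 | 0 (the diabetes row has E1121) |

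No other code in the diabetes row occurs more than 4 times. The appendix prints no sub-headings. Reading the row as ten clusters of neighbouring codes, E1165 is in 10 of 10 and E1065 in 9 of 10, being absent from the cluster around E1100. E1129, E1029 and E1021 occur only in the cluster that matches the kidney row, so they are not part of the problem.

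**Size: assumptions.** The documents give no prevalences or code frequencies. Assume true kidney disease 4% to 8%, diabetes 12% to 15%, and 20% to 40% of diabetics with an E1165 or E1065 claim in a year coded wholly in ICD-10. Assume also that ICD-10 coding began on 1 October 2015 and that index dates are uniform over the window.

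**Step 1, a baseline wholly in ICD-10.** False positives = diabetes × share with either code × (1 − true kidney disease).
- Low: 0.12 × 0.20 × 0.92 = 0.0221
- High: 0.15 × 0.40 × 0.96 = 0.0576

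**Step 2, who has such a baseline.** The index window in Section 8.2.1 (January 2014 to September 2016) has 365 + 365 + 274 = 1,004 days. With a 360-day pre-index period, only index dates from 25 to 30 September 2016 have a baseline wholly after 1 October 2015: 6 of 1,004 days. Step 1 therefore cannot be quoted for the study as a whole.

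**Step 3, share of baseline time in ICD-10.** An index date k days after 1 October 2015 (k = 0 to 365) has min(k, 360) ICD-10 baseline days.
- Sum = 360 × 361 / 2 + 5 × 360 = 66,780
- Total baseline days = 1,004 × 360 = 361,440
- Share = 66,780 / 361,440 = 18.5%

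**Step 4, study-wide size.**
- Proportional to ICD-10 time: 0.0221 × 0.185 = 0.4%, to 0.0576 × 0.185 = 1.1%.
- Ceiling, if every index date from 1 October 2015 carried the full rate (366 / 1,004 = 36.5%): 0.0221 × 0.365 = 0.8%, to 0.0576 × 0.365 = 2.1%.

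Step 1 treats kidney disease as no commoner in diabetics than in others. If it is commoner, these figures are too high.

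**Anxiety.** The ICD-10 cell has 41 distinct codes, of which 10 are R codes. No size can be given from the documents.

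**The case against.** The strongest reply is that the consequence is small. The flags describe baseline and may enter models; they do not define persistence, cost or effectiveness. Diabetes has its own flag, and a Charlson score is calculated separately. That stands, and it keeps the point minor. It does not make the kidney rule right as written.

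A reader might infer that a large part of the kidney flag is false. Under the assumptions above, a wholly ICD-10 baseline gives 0.0221 / (0.0221 + 0.08) = 22% to 0.0576 / (0.0576 + 0.04) = 59% of flagged patients. That baseline exists for only 6 of 1,004 index days, so the figure does not describe this study.

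A reader might also infer that the flags change meaning with index date and make later-starting cohorts look sicker. The documents do not support this. The ICD-9 cell for kidney disease is blank in the text available and the one for anxiety breaks off at a comma, probably through PDF reading, so the two coding eras cannot be compared. No index-date distribution by cohort is given; the approval date of the XR formulation does not supply one. Both arms of the out-of-pocket comparison are tofacitinib users. Index month and year is itself a Section 8.3 variable, so calendar drift can be seen and adjusted for.

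On anxiety, the documents label no R code, and Appendix 4 also uses R codes for kidney disease (R803, R809), liver disease (R17, R168) and sleep disorders (R0681). A deliberately broad definition is possible, so this half stands only as a question to the sponsor.

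**Conclusion.** The kidney point holds on the documents alone: as written, one E1165 or E1065 claim in the 12-month baseline sets the kidney flag, although the appendix attaches those codes to nearly all its diabetes clusters. It applies to those two codes only. Its likely size is about 0.4% to 1.1% of all patients, and at most about 0.8% to 2.1%, resting on the assumed prevalences, uniform index dates and an October 2015 start for ICD-10. It touches Table 3 and candidate covariates, not the definition of the primary outcome. E121 against E1121 may be a typing or PDF-reading slip and needs only a check. The anxiety R codes are a secondary check of unknown size. This is a worthwhile tidy-up, not a threat to the main comparison.

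**What to change.** - Delete E1165 and E1065 from the kidney disease row. Keep E1129, E1029, E1021 and the other listed codes.
- At the same time, check E121 against the diabetes row's E1121. If E121 is a slip for E1121, patients whose only renal code is E1121 would be missed once the two shared codes are gone.
- Confirm whether each of the ten R codes was meant to set the anxiety flag alone. If not, remove them or require an F code alongside.
- Optionally, tabulate each flag's prevalence by quarter of index date.

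The cost is a code-list edit and, if wanted, one frequency table. For kidney disease nothing of substance is lost, because the specific codes remain. For anxiety, the price of narrowing the list is losing any patients recorded only through the R codes (those coded only by symptoms, if R codes are read as symptom codes).
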